12.4 List of Abbreviations and Definition of Terms

Term	Definition
AE	Adverse event
ART	Antiretroviral therapy
ASaT	All Subjects as Treated (population)
CFR	Code of Federal Regulations
CI	Confidence interval
CRF	Case report form
CSR	Clinical study report
DAA	Direct-acting antiviral
DNA	Deoxyribonucleic acid
EBR	Elbasvir
ECI	Events of Clinical Interest
eCRF	Electronic case report form
EDC	Electronic Data Capture
EU	European Union
FAS	Full Analysis Set
FDA	Food and Drug Administration, USA
FDAAA	Food and Drug Administration Amendments Act
FDAMA	Food and Drug Administration Modernization Act
FDC	Fixed-dose combination
FU	Follow-up
FW	Follow-up Week
GCP	Good Clinical Practice
GCS	Global Clinical Supplies
GZR	Grazoprevir
HCC	Hepatocellular carcinoma
HCV	Hepatitis C virus
HIV	Human Immunodeficiency Virus
IB	Investigator's Brochure
ICF	Informed Consent Form
ICH	International Conference on Harmonisation of Technical Requirements for Registration of Pharmaceuticals for Human Use
IEC	Independent Ethics Committee
IFN	Interferon
IL28B	Interleukin-28B (Interferon-lambda 3)
IRB	Institutional Review Board
IVRS	Interactive voice response system
IWRS	Integrated web response system
LLOQ	Lower Limit of Quantification
mFAS	Modified full analysis set
NA, N/A	Not applicable
NI	Nucleotide-Mimetic NS5B Polymerase Inhibitor
NNI	Non-Nucleoside NS5B Polymerase Inhibitor
OBV	Ombitasvir
Peg-IFN	Pegylated Interferon alfa-2b
PGx	Pharmacogenomics
PI	Protease Inhibitor
RAV	Resistance-associated variants
RBC	Red Blood Cell
RBV	Ribavirin

Term	Definition
RNA	Ribonucleic Acid
SAE	Serious Adverse Event
SMD	Study Medication Diary
SOP	Standard Operating Procedure
SVR	Sustained Virologic Response
SVR ₁₂	(Sustained Virologic Response 12 weeks after the end of all study therapy): The subject has HCV RNA <25 IU/mL (either TD(u) or TND) 12 weeks after the end of all study therapy
SVR ₂₄	(Sustained Virologic Response 24 weeks after the end of all study therapy): The subject has HCV RNA <25 IU/mL (either TD(u) or TND) 24 weeks after the end of all study therapy
TE	Treatment-experienced
TN	Treatment-naïve
TND	Target Not Detected (HCV RNA not detected)
TD (u)	Target detected but unquantifiable
TD (q)	Target Detected, quantifiable
TW	Treatment Week
US	United States

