3.1 Primary Objective(s) & Hypothesis(es)

- (1) To evaluate the efficacy of each treatment arm of EBR/GZR as assessed by the proportion of subjects achieving SVR₁₂ [sustained virologic response defined as HCV RNA < Lower Limit of Quantitation (LLOQ) 12 weeks after the end of all study therapy].
- (2) To evaluate the safety and tolerability of EBR/GZR.

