4.2.3.1.1 Measurement of HCV RNA

HCV RNA levels in plasma will be measured on blood samples drawn from each subject at various time points prior to, during, and after dosing, as indicated in the Trial Flow Chart (Section 6.0). Samples are collected and processed as per instructions provided by the central laboratory manual (assay type indicated in central laboratory manual).

Results from the sample collected at the screening visit are used to determine eligibility. Samples collected at other time points are used for efficacy analyses. They are also used to identify subjects who meet virologic failure criteria.

The nomenclature detailed in [Table 9](#) will be used when describing HCV RNA levels:

Table 9 Nomenclature for Describing HCV RNA Levels

Abbreviation	Definition	HCV RNA Level
TND	Target not detected	HCV RNA not detected
TD(u)	Target detected but unquantifiable	HCV RNA < LLOQ
TD(q)	Target Detected, quantifiable	HCV RNA \geq LLOQ

4.2.3.1.1.1 Definition of Efficacy Endpoints

Efficacy will be defined at different time points during the trial. Specific endpoints are:

- SVR₁₂ (sustained virologic response 12 weeks after the end of all study therapy). The subject has HCV RNA < LLOQ (either TD[u] or TND) 12 weeks after the end of all study therapy.
- SVR₂₄ (sustained virologic response 24 weeks after the end of all study therapy). The subject has HCV RNA < LLOQ (either TD[u] or TND) 24 weeks after the end of all study therapy.

4.2.3.1.1.2 Definition of Virologic Failure: Non-Response, Rebound, Virologic Breakthrough and Relapse

Lack of efficacy at different time points in the trial will be categorized as:

- Non-response: Subject has HCV RNA detected at end of treatment without HCV RNA $<$ LLOQ on treatment (note that breakthrough is captured below).
- Rebound: Subject has a rebound defined as $>1 \log_{10}$ IU/mL increase in HCV RNA from nadir while on treatment and confirmed from a separate blood draw within 2 weeks.
- Virologic breakthrough: Subject has a confirmed HCV RNA \geq LLOQ (TD [q]) after being $<$ LLOQ previously while on treatment. Confirmation is defined as an HCV RNA \geq LLOQ from a separate blood draw repeated within 2 weeks.
- Relapse: Subject has a confirmed HCV RNA \geq LLOQ (TD [q]) following end of all study therapy, after becoming undetectable (TND) at end of treatment. Confirmation is defined as an HCV RNA \geq LLOQ from a separate blood draw repeated within 2 weeks.

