7.1.3.2 HCV Evaluation

The following specimens are to be obtained for HCV evaluation as part of efficacy/pharmacogenetic measurements:

- Samples for HCV genotype evaluation must be obtained for inclusion in the study. All baseline samples will be genotyped using the FDA-approved Abbot HCV Real Time Genotype II assay that detects HCV genotypes 1a, 1b, 2, 3, 4, 5, and 6 through the use of genotype-specific fluorescent-labeled oligonucleotide probes in a real-time PT-PCR assay. The RT-PCR reaction uses 3 sets of HCV-specific amplification primers targeting the 5'UTR (for all genotypes) and NS5B regions from GT1a and 1b. The assay has accuracy of > 96% for GT1, 1a, 1b, 2, 3, and 5; 89% for GT5, and 83% for GT6; with 100% specificity in HCV serologically negative plasma samples.
- Blood must be drawn from each subject to assess HCV RNA plasma levels at various time points as shown in the Trial Flow Chart (Section 6.0). HCV RNA in plasma will be measured using a COBAS™ AmpliPrep/COBAS™ Taqman HCV Test, version 2.0® assay with a lower limit of quantification (LLOQ) of 15 IU/mL. Leftover plasma may be used for viral resistance testing if needed. Also, leftover plasma may be used for FBR only if the subject signed for FBR consent.
- Blood must be drawn from each subject to assess viral resistance mutation and processed as instructed by the central laboratory manual. Leftover plasma may be used for FBR only if the subject signed for FBR consent.
- Protein and metabolites may be measured from blood samples to compare biomarkers measured prior to treatment, to biomarkers measured at several time points during treatment that correlate with subject response to treatment (e.g., sustained viral response).
- Samples collected for genetic analysis are obtained at Day 1. Any leftover deoxyribonucleic acid (DNA) may be used for FBR only if the subject sign for FBR consent.

NOTE: Samples may also be used for future assay development and validation if the subject signed for FBR consent.

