8.4.1 Efficacy/Pharmacokinetics Endpoints

8.4.1.1 Efficacy Endpoints

An initial description of efficacy measures is provided in Section 4.2.3.1.

The primary efficacy endpoint is the proportion of subjects achieving SVR₁₂ (sustained virologic response 12 weeks after the end of all study therapy), defined as HCV RNA < LLOQ (either TD[u] or TND).

The secondary efficacy endpoints are:

- The proportion of subjects achieving SVR₁₂, defined as HCV RNA < LLOQ (either TD[u] or TND) in the treatment-naïve F0-F2 subjects.
- The proportion of subjects achieving SVR₂₄ (sustained virologic response 24 weeks after the end of all study therapy), defined as HCV RNA < LLOQ (either TD[u] or TND).
- The viral resistance-associated variants (RAVs) resistant to EBR or GZR, including the association of baseline RAVs with treatment outcomes (SVR₁₂ and SVR₂₄) and the emergence of RAVs in subjects who fail to achieve SVR.

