8.6.1 Statistical Methods for Efficacy Analyses

This section describes the statistical methods that address the primary and secondary objectives.

Missing Values

A missing data point for a given study visit may be due to any of the following reasons: a visit occurred but data were not collected or were unusable; a visit did not occur; or a subject discontinued from the study before reaching the visit. Subjects who prematurely discontinued the assigned treatment are encouraged to remain in the study for follow-up, if possible.

The HCV RNA outcome is categorized as TND (Target not detected), TD(u) (Target detected but unquantifiable), and TD(q) (Target detected, quantifiable). There are 3 types of missing data handled by different approaches.

Type 1 is intermittent missing:

- Intermittent missing: If a missing data point is immediately preceded and followed by non-missing HCV RNA outcomes, the missing value would be imputed to the worst outcome of the two. For example, if a missing data point is preceded by TD(q) and followed by TD(u) or TND, then the missing value would be imputed as TD(q); if a missing data point is preceded by TD(u) and followed by TND, then the missing value would be imputed as TD(u); when a missing value is flanked by 2 TNDs, then the missing value would be imputed as TND.

Type 2 and 3 are both non-intermittent missing, but differ regarding their relationship to the study drug:

- Type 2 – Non-intermittent missing related to the study drug: For missing values due to premature study discontinuations due to treatment related reasons either for safety or efficacy, the missing values will be considered as treatment failures.
- Type 3 – Non-intermittent missing unrelated to the study drug: For missing data due to premature study discontinuations with reasons unrelated to treatment such as loss to follow-up, protocol violation, withdrawal of consent, administrative reasons, etc., the missingness mechanism is unlikely to be related to subjects' response to the HCV treatment, and therefore the missing at random (MAR) assumption is reasonable. The approaches to address this type of missing data depend on the analytical strategy, and these are described as follows.

The following 2 approaches will be used to handle non-intermittent missing data (Type 2 and 3) due to premature discontinuations, depending on the analytical strategy, as described in the following section and [Table 14](#) Analysis Strategy for Efficacy Variables.

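### Does the 25 IU/mL figure in the Section 12.4 glossary put the definition of SVR12 and SVR24 in doubt?

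*Combined protocol and SAP*

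**What the plan says.** The two glossary entries in Section 12.4 carry a number. For SVR12: "The subject has HCV RNA <25 IU/mL (either TD(u) or TND) 12 weeks after the end of all study therapy". For SVR24: "The subject has HCV RNA <25 IU/mL (either TD(u) or TND) 24 weeks after the end of all study therapy".

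The sections that govern the analysis tie response to the assay limit:

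- Section 3.1, primary objective: "sustained virologic response defined as HCV RNA < Lower Limit of Quantitation (LLOQ) 12 weeks after the end of all study therapy". Section 3.2 treats SVR24 in the same way.
- Section 4.2.3.1.1.1, endpoint definitions: "The subject has HCV RNA < LLOQ (either TD[u] or TND) 12 weeks after the end of all study therapy", with a parallel sentence for SVR24.
- SAP Section 8.4.1.1, which points back to Section 4.2.3.1 for the description of the efficacy measures: "defined as HCV RNA < LLOQ (either TD[u] or TND").
- Table 15 in SAP Section 8.6.1 has a result below LLOQ as the response criterion in both the FAS and the mFAS row.
- SAP Section 8.6.1 handles HCV RNA as three categories: "TND (Target not detected), TD(u) (Target detected but unquantifiable), and TD(q) (Target detected, quantifiable").

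On the assay, Section 7.1.3.2 names an "assay with a lower limit of quantification (LLOQ) of 15 IU/mL", while Section 4.2.3.1.1 says "assay type indicated in central laboratory manual". The summary table in Section 8.1 names both endpoints without a threshold.

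**The concern.** SVR12 is the primary endpoint and SVR24 the key secondary endpoint, so two different cut-offs for them in one document deserve a check. The glossary sentences are nearly those of Section 4.2.3.1.1.1, with a number in place of LLOQ, and that number is not the LLOQ stated for the assay. Section 1.0 sends readers to Section 12.4 for abbreviations, and the section's title says that it also defines terms. It is the only place where the SVR cut-off itself appears as a figure, so a programmer or author looking for a number might take it from there.

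If 25 IU/mL were applied on its own, a subject with 20 IU/mL at follow-up week 12 would count as SVR12. Under Table 9 and an LLOQ of 15 that result is quantifiable, so the FAS row of Table 15 makes it a non-response. If the subject had been target-not-detected at the end of treatment and the result was confirmed, Section 4.2.3.1.1.2 would call it a relapse. The same person could then be both a responder and a virologic failure in the resistance population of Section 8.5.1, which is built from those two groups.

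**Working it through.** **Step 1. Which rule the analysis uses.** Sections 3.1, 3.2, 4.2.3.1.1.1 and 8.4.1.1 and Table 15 all give response as below LLOQ. Section 8.4.1.1 refers to Section 4.2.3.1. Nothing in Section 8 refers to Section 12.4 for a threshold. The missing-data rules in Section 8.6.1 work on categories, so no figure from the glossary enters there either.

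**Step 2. Which results each rule accepts.** The LLOQ is 15 IU/mL (Section 7.1.3.2) and the categories are those of Table 9. The glossary has two conditions: below 25, and TD(u) or TND.

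| HCV RNA result | Category | SAP: below LLOQ | Glossary, both conditions | 25 IU/mL alone |
|---|---|---|---|---|
| Not detected | TND | response | response | response |
| Detected, below 15 | TD(u) | response | response | response |
| 15 to below 25 | TD(q) | non-response | non-response | response |
| 25 or more | TD(q) | non-response | non-response | non-response |

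The third and fourth columns agree in every row. A TD(u) or TND result is below 15 and therefore below 25, so the 25 excludes nobody whom the qualifier admits. It is redundant. This also holds at any LLOQ up to and including 25 IU/mL. (Table 15's mFAS row separately counts a result at or above LLOQ as response when it is shown to be reinfection. That footnote does not depend on which cut-off is used.)

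**Step 3. Size of the hypothetical misreading.** The last column differs from the SAP only for 15 to below 25 IU/mL. One subject in that band moves the rate by 100/n points:

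- Arm 1: 100/50 = 2.0 (at the minimum of 40, 100/40 = 2.5)
- Arm 2: 100/70 = 1.4
- Arm 2, treatment-naïve F0-F2: 100/25 = 4.0 (at the minimum of 20, 100/20 = 5.0)

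**Step 4. Intervals.** The Clopper-Pearson limits for x responders out of n are the 0.025 quantile of Beta(x, n − x + 1) and the 0.975 quantile of Beta(x + 1, n − x). This formula reproduces all 13 rows of Table 17 to 0.1 point. Table 17 does not depend on the cut-off. For one misclassified subject, with illustrative counts:

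| Group | SAP rule | 25 IU/mL alone |
|---|---|---|
| Arm 1 | 48/50 = 96.0% (86.3, 99.5) | 49/50 = 98.0% (89.4, 99.9) |
| Arm 2 | 68/70 = 97.1% (90.1, 99.7) | 69/70 = 98.6% (92.3, 100.0) |
| Arm 2, treatment-naïve F0-F2 | 23/25 = 92.0% (74.0, 99.0) | 24/25 = 96.0% (79.6, 99.9) |

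The documents do not say how many results fall between 15 and 25 IU/mL. With none, even the misreading changes nothing.

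**The case for a change.** The strongest case for acting is that a wrong number in a written definition of the primary endpoint should not stand when correcting it takes two lines. The assay is also not fully fixed, because Section 4.2.3.1.1 leaves its type to the central laboratory manual while Section 7.1.3.2 names one. On that view the document carries two figures, 15 and 25, and defers to a third source.

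Part of this stands. The 25 agrees with no LLOQ in the document, and it is sensible to tidy it when the text is next opened. The rest does not carry weight. The entry is not self-contradictory: its two conditions can hold together, and jointly they give the SAP's answer. The laboratory manual point cuts the other way, because a rule written as below LLOQ follows whatever limit the assay has, and no error in the manual is shown. The route to harm needs three things at once: taking the cut-off from an abbreviation list over the SAP, ignoring the qualifier in the same sentence, and having a subject in a 10 IU/mL band (25 − 15). No section directs the first two, and the documents give no frequency for the third.

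**Conclusion.** This is a clerical slip in the glossary with no effect on the planned results. Following the SAP, or following the glossary entry in full, yields the same SVR12 and SVR24 counts, so the shift is 0 points in either arm and in the treatment-naïve F0-F2 group. The shifts of 1.4 to 5.0 points per subject describe a misreading and not the plan.

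The conclusion rests on two things in the text: the SAP's rule governs, and the glossary's TD(u) or TND qualifier is read as part of its definition. It also assumes that the assay's LLOQ is the stated 15 IU/mL, although the equivalence would hold for any limit up to 25. Correcting the entries would be editorial and would alter no endpoint, analysis, sample size or interval, so no change to the plan is called for.

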12.5 Approximate Blood/Tissue Volumes Drawn/Collected by Trial Visit and by Sample Types

	Screening	Day 1	Week 4	Week 8	Week 12	FW 4	FW 12	FW 24	Total Volume
Test	Approximate Blood Volume (mL)								
Coagulation (PT, INR)	4.5	4.5	4.5	4.5	4.5	4.5	4.5	4.5	36
HBV Evaluations (HBsAg, Anti-HBc, Anti-HBs, HBV DNA) ¹	10	10	10	10	10	10	10	10	80
HIV-1 Serology	6								6
Chemistry	10		10	10	10	10	10	10	80
Hematology	3	3	3	3	3	3	3	3	24
Follicle Stimulating Hormone (FSH)	2								2
HCV Genotype Determination	4								4
HCV Viral Resistance and biomarkers		6				6	6	6	24
HCV RNA	10	10	10	10	10	10	10	10	80
HIV RNA	6								6
CD4+ T-cell count	6								6
Blood for Genetic Analysis		8.5							8.5
Expected Total (mL) Main Study Population	61.5	52	37.5	37.5	37.5	43.5	43.5	43.5	356.5

Anti-HBc=hepatitis B core antibody; anti HBs=hepatitis B surface antibody; GT = genotype; HBsAg=hepatitis B surface antigen; HBV DNA=hepatitis B virus deoxyribonucleic acid; HCV=hepatitis C virus; HIV=Human immunodeficiency virus; INR=international normalized ratio; PT=prothrombin time.

¹ HBsAg, anti-HBc, and anti-HBs will be assessed at screening in all subjects. For all anti-HBc positive subjects, HBV DNA will also be assessed at screening, and both HBV DNA and HBsAg will be monitored during the trial.

